6.2.1.4 Dose-limiting Toxicities

Dose-limiting toxicities are defined as any adverse event with an onset within first following first dose of tarlatamab with any of the following criteria unless clearly related to causes other than tarlatamab:

All grade 3 adverse events except

Protocol Number: 20200439

Date: 05 June 2024 Page 59 of 176

Fatigue lasting less than 7 days

- Grade 3 non-febrile neutropenia that improves to ≤ grade 1 within 3 weeks including the use of growth factor support per neutropenia management guidelines (see Section 6.8.5)
- Endocrinopathies, if manageable with replacement therapy
- Grade 3 nausea/vomiting or diarrhea for less than 72 hours with adequate antiemetic and other supportive care
- Grade 3 amylase or lipase values that are not associated with symptoms or clinical manifestations of pancreatitis
- Grade 3 hematologic lab abnormalities that are not considered clinically relevant
- Grade 3 electrolyte abnormality that lasts up to 72 hours, is not clinically complicated, and resolves spontaneously or responds to conventional medical interventions
- Grade 4 adverse event regardless of duration, except:
 - Grade 4 non febrile neutropenia lasting less than or equal to 7 days including the use of growth factor support per neutropenia management guidelines (see Section 6.8.5)
 - Grade 4 electrolyte abnormality that lasts up to 72 hours, is not clinically complicated, and resolves spontaneously or responds to conventional medical interventions
 - Grade 4 amylase or lipase values that are not associated with symptoms or clinical manifestations of pancreatitis
 - Grade 4 hematologic lab abnormalities that are considered not clinically relevant
- Grade 5 adverse events
- Recurrent grade 2 or higher pneumonitis
- Without exception, any other toxicity requiring permanent discontinuation of AMG 404 per Table 6-2.

The following adverse events will NOT be adjudicated as DLT regardless of the grade or duration:

- Lymphopenia
- Fever
- Tumor lysis syndrome including associated manifestations attributable to TLS (eg, electrolyte abnormalities, renal dysfunction, hyperuricemia)
- 6.2.2 Dosage Adjustments, Delays, Rules for Withholding or Restarting, Permanent Discontinuation

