6.2.2.1.2 Dose Delays

During the first DLT observation period, if the dosing of tarlatamab is delayed for more than 72 hours for reasons other than DLT during the DLT evaluation period, a replacement subject may be enrolled and assigned to the same dose level. The subject may continue on study only after discussion with the Medical Monitor.

After the DLT observation period, if the dosing of tarlatamab is delayed for ≤ 2 weeks, the subject should resume the treatment as soon as possible if deemed safe by the investigator. If the dosing of tarlatamab is delayed between 2 to 4 weeks due to severe or life-threatening treatment-related adverse events, the subject can resume treatment if the toxicities resolve to grade ≤ 1 or return to subjects' baseline values within 3 weeks and restarting of therapy has been deemed safe by the investigator and medical monitor.

If the dosing of tarlatamab is delayed for more than 4 weeks due to severe or life-threatening treatment-related adverse events, the subject will be discontinued from investigational product. If the dosing delay occurred under other conditions, the case will be reviewed by the sponsor to determine whether and when the subject will be allowed to resume tarlatamab.

Protocol Number: 20200439

Date: 05 June 2024 Page 61 of 176

For adverse events related to CRS, neurological events, and pituitary dysfunction, please see Sections 6.8.1, 6.8.3, and 6.8.4 respectively for guidelines for dose delays.

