6.2.2.1.3 Rules for Withholding or Restarting

Tarlatamab should be withheld for any of the following:

- DLT
- Symptomatic hypophysitis (See Section 6.8.4)
- Criteria for conditional withholding of tarlatamab due to potential hepatotoxicity (Section 11.7)

Tarlatamab dosing can be resumed if the toxicities resolve to grade \leq 1 or return to subjects' baseline values within 3 weeks. The restarting of therapy should be deemed safe by the investigator and medical monitor.

Subjects should not be restarted with tarlatamab if the following treatment-related adverse events occur:

- Criteria for permanent withholding of tarlatamab due to potential hepatotoxicity (Section 11.7)
- Any grade ≥ 4 adverse events except those not considered DLT as described in Section 6.2.1.4
- Grade 3 adverse event(s) that do not recover to grade ≤ 1 within 3 weeks
- Any grade 3 adverse events that recur (with the exception of grade 3 laboratory parameters not considered clinically relevant or recurrent non-febrile grade 3 neutropenia which resolves with supportive care to grade ≤ 1 or returns to subjects' baseline values within 3 weeks)

For adverse events related to CRS, neurological events and pituitary dysfunction, please see Sections 6.8.1, 6.8.3, and 6.8.4 respectively for guidelines for dose adjustment.

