1	Symptoms are not life threatening and require symptomatic treatment only, eg, fever, nausea, fatigue, headache, myalgias, malaise	Administer symptomatic treatment (eg, paracetamol/acetaminophen for fever). Monitor for CRS symptoms including vital signs and pulse oximetry at least Q2 hours for 12 hours or until resolution, whichever is earlier.	N/A
2	Symptoms require and respond to moderate intervention Oxygen requirement < 40%, OR Hypotension responsive to fluids or low dose of one vasopressor, OR grade 2 organ toxicity or grade 3 transaminitis per CTCAE criteria	 Administer: Symptomatic treatment (eg, paracetamol/acetaminophen for fever) Supplemental oxygen when oxygen saturation is < 90% on room air Intravenous fluids or low dose vasopressor for hypotension when systolic blood pressure is < 85 mmHg. Persistent tachycardia (eg, > 120 bpm) may also indicate the need for intervention for hypotension. Monitor for CRS symptoms including vital signs and pulse oximetry at least Q2 hours for 12 hours or until resolution to CRS grade ≤ 1, whichever is earlier. For subjects with extensive co-morbidities or poor performance status or if CRS does not resolve to grade ≤ 1 in 48 hours, manage per grade 3 CRS guidance below. 	If CRS occurs during tarlatamab treatment, immediately interrupt the infusion and delay the next tarlatamab dose until the event resolves to CRS grade ≤ 1 for no less than 72 hours. Resume tarlatamab at same dose or reduce to next lower dose, if clinically indicated. (continuation with the next planned dose may be allowed after discussion with the medical monitor). Permanently discontinue tarlatamab if there is no improvement to CRS ≤ grade 1 within 7 days.

Protocol Number: 20200439

Date: 05 June 2024 Page 76 of 176

Table 6-4. Grading and Management of Cytokine Release Syndrome

	Table 6-4. Grading and Management of Cytokine Release Syndrome				
CRS Grade	Description of Severity ^a	Minimum Expected Intervention	Instructions for Dose Modifications of Tarlatamab		

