9.3 Populations for Analysis

The following populations are defined:

Population	Description
Enrolled	All subjects who sign the ICF
Safety	The Safety Analysis Set will consist of all subjects who received at least 1 dose of any Investigational Products. The analysis of all safety and efficacy endpoints, unless noted otherwise, will be conducted on the Safety Analysis Set.
DLT	For the dose exploration part of the study, the analysis of DLT will be conducted on the DLT Analysis Set, defined as all subjects that are enrolled and received at least 1 dose of tarlatamab and AMG 404 with an evaluable DLT endpoint. The DLT endpoint is evaluable if either: 1) the subject experiences a DLT, or 2) the subject does not experience a DLT and receives tarlatamab and AMG 404 treatment as

98

[figure not shown]
Protocol Number: 20200439

Date: 05 June 2024 Page 107 of 176

	planned in cycle 1 and has been followed for safety events a minimum of from start of treatment.
OR	The OR Analysis Set will consist of all subjects in the Safety Analysis Set who have had the opportunity to be followed for at least 8 weeks starting from day 1.
PK	The PK Analysis Set will contain all subjects who have received at least 1 dose of the Investigational Product and have at least 1 PK sample collected. These subjects will be evaluated for PK analysis unless the number of data points required for analysis is not enough, or significant protocol deviations have affected the data, or if key dosing or sampling information is missing.

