9.4.1 Planned Analyses

9.4.1.1 Interim Analysis and Early Stopping Guidelines

Safety data will be reviewed on an ongoing basis.

During dose exploration (Part 1) and formally during DLRMs, Amgen, in consultation with the site investigators, will review all available cumulative data by cohort prior to making dose escalation or dose de-escalation recommendation. Adverse events and DLTs observed in all subjects will be evaluated continually and fully integrated into all DLRMs and considered in all enrolment and dosing decisions.

Protocol Number: 20200439

Date: 05 June 2024 Page 108 of 176

During dose expansion (Part 2), Amgen will conduct evaluations of the ongoing grade 4 or higher treatment-related **treatment emergent adverse events** to assess if the threshold for possible early trial termination has been reached. The safety interim will occur for every subjects enrolled who have had opportunity to have at least days of follow up since the first dose of tarlatamab. If this threshold is met, enrollment to dose expansion will be halted pending review of safety data by the DLRT. After receiving the DLRT recommendation, Amgen will choose to take one of the following actions.

- 1) Terminate the trial
- 2) Amend the protocol to potentially improve the benefit/risk for subjects (eg, increase safety monitoring, modify dose/schedule, mandate premedication)
- 3) Continue dose expansion without any changes.

The stopping rules use a Bayesian approach proposed by Thall (Thall et al, 1995) to terminate the study if the posterior probability that the grade 4 or higher treatment-related **treatment emergent adverse event** rate is greater than 20% is > 80%. The stopping boundaries assume a prior distribution of Beta (0.40, 1.60) are presented in Table 9-2 and the operating characteristics with pre-specified batch size of new subjects per batch are presented in Table 9-3.

Table 9-2. Stopping Boundary for Dose Expansion with Posterior Probability of 80% and Grade 4 or Higher Treatment-related Adverse Event Limit of 20%

Number of Subjects	Stop Subjects if Observing This Many Grade 4 or Higher Treatment-related Adverse Events	
	≥ 4	
	≥ 6	
	≥ 9	
	Dose Expansion Complete	

Table 9-3 Operating Characteristics with Batch Size of Subjects

True Grade 4 or Higher Treatment-related Adverse Event Rate	Probability of Early Stopping of Dose Expansion	Average Dose Expansion Sample Size
0.10	2.0%	39.5
0.15	9.7%	37.6
0.20	25.8%	33.9
0.25	47.7%	28.8

Protocol Number: 20200439

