6.3 DLT Analysis Set

For the dose exploration part of the study, the analysis of DLT will be conducted on the DLT Analysis Set, defined as all subjects that are enrolled and received at least 1 dose of tarlatamab or AMG 404 with an evaluable DLT endpoint. The DLT endpoint is evaluable if either: 1) the subject experiences a DLT, or 2) the subject does not experience a DLT and receives tarlatamab or AMG 404 treatment as planned in cycle 1 and has been followed for safety events a minimum of from date of first dose administration of tarlatamab or AMG 404.

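### A toxicity that permanently stops tarlatamab without meeting a DLT criterion is never counted in the formal DLT rate, and Protocol 9.3 and SAP 6.3 differ on whether the subject stays in the DLT set

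*Protocol*

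**What the plan says.** Protocol 6.2.1.4 sets the DLT floor at grade 3, with listed exemptions. Two criteria reach lower: "Recurrent grade 2 or higher pneumonitis" and "Without exception, any other toxicity requiring permanent discontinuation of AMG 404 per Table 6-2". Table 6-2 concerns AMG 404, the fixed-dose partner. No criterion refers to permanent discontinuation of tarlatamab.

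Other sections stop tarlatamab permanently for events that need not be DLTs. The grade 2 row of Table 6-4 (Protocol 6.8.1) reads: "Permanently discontinue tarlatamab if there is no improvement to CRS ≤ grade 1 within 7 days". Protocol 6.2.2.1.3 bars restart after treatment-related events that include "Any grade 3 adverse events that recur", excepting only laboratory values judged not clinically relevant and resolving non-febrile neutropenia. Some grade 3 events, such as vomiting for under 72 hours, are DLT-exempt in 6.2.1.4.

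The two documents then define evaluability differently for a subject without a DLT. Protocol 9.3 requires that "the subject does not experience a DLT and receives tarlatamab and AMG 404 treatment as" planned in cycle 1. SAP 6.3 requires that "the subject does not experience a DLT and receives tarlatamab or AMG 404 treatment as planned in cycle 1". Protocol 6.2.2.1.2 adds that, when tarlatamab is delayed more than 72 hours in the DLT period for reasons other than a DLT, "a replacement subject may be enrolled and assigned to the same dose level".

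**The concern.** Part 1 escalates tarlatamab while AMG 404 stays fixed. A subject whose toxicity forces a permanent stop of tarlatamab is direct evidence on whether the dose is tolerated. The DLT definition counts such a stop for the partner drug but not for the drug whose dose is being chosen.

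The affected subject is either removed because of toxicity, which is informative exclusion, or kept as having had no DLT. The Table 4-2 decisions, the tabulated DLT incidence (a primary endpoint) and the isotonic estimate behind the RP2D all use the resulting counts, so each can understate intolerance.

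**Working it through.** **1. Route of an affected subject.** Protocol 2.2.2.3 reports that CRS in the first-in-human study came mainly after the first two cycle 1 doses. Protocol 4.1 plans a first step dose, a step dose equal to the target, and a further target dose. A stop before cycle 1 dosing is complete is therefore the usual case.

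| Situation | Protocol 9.3 | SAP 6.3, read literally |
|---|---|---|
| Tarlatamab stopped before the last cycle 1 dose, AMG 404 given as planned | Not evaluable; may be replaced | Evaluable, no DLT |
| Event after the last cycle 1 dose | Evaluable, no DLT | Evaluable, no DLT |
| Event also forces permanent AMG 404 discontinuation under Table 6-2 | DLT | DLT |

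Only the last row counts the toxicity.

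**2. Reproducing Table 4-2.** Inputs (Protocol 4.1 and 9.4.2.5): target 0.30, equivalence interval (0.25, 0.33), prior Beta(1, 1), unsafe if P(rate > 0.30) > 0.95. With x DLTs in n subjects the posterior is Beta(1 + x, 1 + n − x). The decision is the type of the subinterval (width 0.08) with the largest unit probability mass. The column of subject numbers is redacted, but all seven visible blocks match at n = 3, 4, 5, 6, 7 (or 8, same rule), 9 and 10.

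**3. One affected subject.**

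| Dropped | Counted as toxicity |
|---|---|
| 0/3: E | 1/4: S |
| 0/4: E | 1/5: E (no change) |
| 1/5: E | 2/6: D |
| 1/6: E | 2/7: S |
| 2/9: E | 3/10: S |

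1/5 against 2/6 is six treated without replacement; 1/6 against 2/7 is the same case after replacement. The SAP wording can be less cautious still: with two DLTs and one affected subject among nine, dropping gives 2/8 (S), keeping as a non-DLT gives 2/9 (E), and counting gives 3/9 (D).

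**4. Rates.** Let p be the DLT rate and q the share stopping this way. The expected rate is p/(1 − q) if dropped, p if kept as a non-DLT, and p + q if counted. The dropped rate is below p + q whenever p + q < 1. For p = 20% and q = 5%: 0.20/0.95 = 21.1%, 20.0% and 25.0%. With six subjects in the set, escalation means at most one event, so P(E) = (1 − r)^6 + 6r(1 − r)^5 at rate r, which gives 0.630, 0.655 and 0.534.

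**5. How often the decision differs.** Enroll until six are evaluable. The number of affected subjects is k, with probability C(5 + k, k) q^k (1 − q)^6. DLTs among the six are x ~ Binomial(6, p/(1 − q)). Compare the decision at x/6 with that at (x + k)/(6 + k), for p = 20%:

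| q (assumed) | Decision differs | E versus S | E versus D or DU |
|---|---|---|---|
| 2% | 4.7% | 4.4% | 0.3% |
| 5% | 11.9% | 9.5% | 1.9% |
| 10% | 23.7% | 14.6% | 6.5% |

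The remainder is D versus DU. With six treated and no replacement, the totals are 5.6%, 14.0% and 27.8%, mostly E versus D.

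**6. What bounds q.** The documents do not give the share of grade 2 CRS lasting beyond 7 days. In Part A1 of the first-in-human study (Protocol 2.2.2.3), grade 2 or higher CRS of any duration was 9.9%, treatment-related withdrawal over all cycles was 3.7%, and one serious CRS event led to discontinuation (one subject is 1.2%). In Part A2 no CRS led to discontinuation. At q = 1.2% the step 5 model gives 2.8%.

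**The case against.** The strongest reply is that these toxicities are seen and acted on. Under Protocol 9.4.1.1, adverse events and DLTs in all subjects are "evaluated continually and fully integrated into all DLRMs and considered in all enrolment and dosing decisions". Section 6.2.1.2 has the review team weigh the cumulative adverse event profile, and Appendix 3 (11.3) requires a unanimous vote to escalate. SAP 9.6.2 tabulates adverse events leading to discontinuation by cohort. This stands for the live decisions: Table 4-2 is a guide, and the probabilities above describe the algorithm alone. It does not repair the tabulated DLT incidence or the isotonic estimate, which use observed DLT rates only.

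A reader might infer that every such subject becomes non-evaluable and is lost from dose finding. The documents do not support that: SAP 6.3 can keep the subject, and an event after the last cycle 1 dose leaves the subject evaluable under both documents.

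The range of triggering events is also narrower than it may appear. Table 6-2 already stops AMG 404 for recurrence of the same grade 3 immune-related reaction, so those events are DLTs and only non-immune recurrences remain. A stop under Table 11-3 driven by INR with raised transaminases is unclear rather than plainly a non-DLT: that table covers Amgen investigational product, and Table 6-2 refers to Section 11.7. A grade 2 CRS event with a component that itself meets a DLT criterion is also already counted. The instruction in the grade 2 row to manage persistent CRS under grade 3 guidance does not close the gap, because it changes management and not the grade.

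Finally, enrollment ended in January 2023 (Protocol 4.1). Redefining a primary endpoint now, with open-label data in hand, would be post hoc. That is a sound objection to rewriting the DLT criteria, and it shapes the fix.

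**Conclusion.** The gap holds. On no route does the formal DLT rate or the isotonic estimate count a toxicity that permanently stops tarlatamab without meeting a DLT criterion or forcing AMG 404 discontinuation under Table 6-2. Protocol and SAP also disagree on whether the subject stays in the denominator. The DLT rate is therefore understated as a measure of tolerability.

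The size is unknown. The figures of 4.7%, 11.9% and 23.7% rest on an assumed q of 2% to 10%, a true DLT rate of 20%, one look at six evaluable subjects with replacement, and decisions that follow Table 4-2 exactly. The Part A1 withdrawal figure of 3.7%, not limited to cycle 1 or to events below DLT grade, suggests the lower part of that range is more plausible.

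A reader might go further and conclude that the chosen dose is wrong, or that escalation was unsafe. Nothing in the documents shows that any Part 1 subject was affected, and the review team saw all adverse events. Severity is moderate, not must-fix.

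**What to change.** 1. Reconcile Protocol 6.2.1.4, Table 6-4, 6.2.2.1.3, Protocol 9.3 and SAP 6.3. Use one DLT-evaluable definition in both documents, under which a subject who permanently stops tarlatamab for toxicity in the DLT period is neither silently dropped nor counted as having tolerated the dose. No change to a treatment rule is proposed. DLT status also triggers withholding (6.2.2.1.3) and a dose-reduction option (6.2.2.1.1), which is a further reason to leave the clinical criteria to the sponsor.

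2. Keep the protocol-defined DLT analysis as it is. Add to SAP 9.6.1 a sensitivity analysis, labelled as such: list every Part 1 subject whose tarlatamab was permanently discontinued for toxicity in the DLT period, then report DLT incidence and the isotonic estimate by dose level with these subjects in the denominator and counted as toxicities. If there are none, one sentence in the report settles the matter.

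The cost is a wording change, one extra table, and a tolerability figure that may be slightly less favourable.

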3	Symptoms require and respond to aggressive intervention • Oxygen requirement ≥ 40%, OR • Hypotension requiring high dose ^b or multiple vasopressors, OR grade 3 organ toxicity or grade 4 transaminitis per CTCAE criteria	Admit to intensive care unit for close clinical and vital sign monitoring per institutional guidelines. Administer dexamethasone (or equivalent) IV at a dose maximum of 3 doses of mg mg/day). The dose should then be reduced step-wise. Investigators should consider use of tocilizumabo mg/kg over 1 hour (not to exceed mg). Repeat tocilizumabo every 8 hours as needed if not responsive to IV fluids or increasing supplemental oxygen. Maximum of 3 doses in a period. Maximum total of 4 doses. Investigators may also consider additional therapy, based on clinical judgment.	If CRS occurs during tarlatamab treatment, immediately interrupt tarlatamab and delay the next dose until event resolves to CRS grade ≤ 1 for no less than 72 hours. Resume tarlatamab to next lower dose (continuation at same dose with dexamethasone premedication may be allowed after discussion with the medical monitor). Permanently discontinue tarlatamab if there is no improvement to CRS ≤ grade 2 within 5 days or CRS ≤ grade 1 within 7 days. Permanently discontinue or reduce to next lower dose of tarlatamab if CRS grade 3 occurs at the initial first step dose.		
4	Life-threatening symptoms Requirement for ventilator support OR grade 4 organ toxicity (excluding transaminitis) per CTCAE criteria	Admit to intensive care unit for close clinical and vital sign monitoring per institutional guidelines. Administer dexamethasone (or equivalent) IV at a dose maximum of 3 doses of mg mg/day). Further steroid use should be discussed with the Amgen medical monitor. Investigators should consider use of tocilizumabo mg/kg IV over 1 hour (not to exceed mg). Repeat tocilizumabo every 8 hours as needed if not responsive to IV fluids or increasing supplemental oxygen. Maximum of 3 doses in a hour period. Maximum total of 4 doses. Investigators may also consider additional therapy, based on clinical judgment.	If CRS occurs during tarlatamab treatment, immediately stop the infusion. Permanently discontinue tarlatamab therapy.		

CRS = cytokine release syndrome; CTCAE = Common Terminology Criteria for Adverse Events;

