^b High dose vasopressors (all doses are required for ≥ 3 hours): Norepinephrine monotherapy ≥ 20 μg/min; Dopamine monotherapy ≥ 10 μg/kg/min, Phenylephrine monotherapy ≥ 200 μg/min, Epinephrine monotherapy ≥ 10 μg/min; If on vasopressin, vasopressin + norepinephrine equivalent of ≥ 10 μg/min; If on combination vasopressors (not vasopressin), norepinephrine equivalent of ≥ 20 μg/min

IV = intravenous; N/A = not applicable

^a Revised grading system for CRS (Lee et al, 2014)

Protocol Number: 20200439

Date: 05 June 2024 Page 77 of 176

c If tocilizumab is not available, siltuximab (an anti-interleukin-6 [IL-6] monoclonal antibody) may be used in the management of cytokine release syndrome, following the criteria outlined in Table 6-4. The recommended dose of siltuximab is mg/kg administered over 1 hour as an intravenous infusion, consistent with the prescribing information for the treatment of multicentric Castleman's disease (Sylvant® Prescribing Information), and the CARTOX Working Group Guidelines for CRS management (Neelapu, 2018). Siltuximab may be repeated if needed, in the event that CRS recurs after a subsequent infusion of tarlatamab. Siltuximab may not be repeated in an individual subject that develops anaphylaxis to siltuximab, or gastrointestinal perforation after siltuximab.

Protocol Number: 20200439

Date: 05 June 2024 Page 78 of 176

Re-start of treatment after CRS:

After a grade 3 CRS event, the next infusion may be administered if all the following criteria are met:

- The Amgen medical monitor must be consulted prior to re-starting treatment
- If CRS occurred during tarlatamab infusion, infusion has been interrupted for at least 72 hours
- The event has resolved to grade ≤ 1 prior to re-starting treatment

If a subject experiences two separate grade 3 CRS events, tarlatamab must be permanently discontinued.

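### After grade 3 CRS, Table 6-4 and the restart list in Section 6.8.1 set different timing conditions for the next tarlatamab dose, and the protocol does not say which governs

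*Protocol*

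**What the plan says.** Both rules are in Protocol Section 6.8.1.

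- **Table 6-4, grade 3 row.** For CRS arising during treatment, the instruction is: "immediately interrupt tarlatamab and delay the next dose until event resolves to CRS grade ≤ 1 for no less than 72 hours". The same row caps recovery time: "Permanently discontinue tarlatamab if there is no improvement to CRS ≤ grade 2 within 5 days or CRS ≤ grade 1 within 7 days".
- **Restart list below the table.** It opens: "After a grade 3 CRS event, the next infusion may be administered if all the following criteria are met". Three criteria follow:
  - The first is a matter of oversight and applies in every case: "The Amgen medical monitor must be consulted prior to re-starting treatment".
  - The second is the list's only condition on elapsed time, and it is conditional: "If CRS occurred during tarlatamab infusion, infusion has been interrupted for at least 72 hours".
  - The third deals with recovery and names no minimum duration: "The event has resolved to grade ≤ 1 prior to re-starting treatment".

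The body text of Section 6.8.1 sends the reader to Table 6-4 for grading and management. Sections 6.2.2.1.1 to 6.2.2.1.3 send CRS cases back to Section 6.8.1. None of these says how the table and the list relate.

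**The concern.** The two texts cover the same event and the same decision but differ in two ways. The first is the start of the clock: the table, read plainly, counts 72 hours at grade 1 or less, while the list counts 72 hours of interruption. The second is the trigger: the table speaks of CRS during treatment, the list of CRS during the infusion. The infusion lasts about 60 minutes, and Section 6.8.1 places the raised risk in the first few days after the initial infusion and after a step increase. Onset after the infusion is therefore an expected case, and for it the list has no 72-hour condition.

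CRS is an identified risk of tarlatamab, and CRS events enter the primary safety endpoint as adverse events. Two sites could reach different earliest dosing times after the same grade 3 event, each with protocol text in support. Dose delays and relative dose intensity, which SAP Section 9.6.8 summarises, would carry that difference.

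**Working it through.** The plan gives no figure to reproduce, so the check compares the two rules.

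**Inputs.** Let R be the hours from onset to grade 1 or less. The documents give no distribution of R, so the values below are assumed. The grade 3 row caps R at 7 days: 7 × 24 = 168 h. For onset during infusion, interruption is counted from onset.

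**Earliest next dose, in hours from onset**
- Table 6-4, plain reading: R + 72.
- List, onset during infusion: max(R, 72).
- List, onset after infusion: R.

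| R (assumed) | Table | List, onset during infusion | Gap | List, onset after infusion | Gap |
|---|---|---|---|---|---|
| 24 | 96 | 72 | 24 | 24 | 72 |
| 60 | 132 | 72 | 60 | 60 | 72 |
| 168 | 240 | 168 | 72 | 168 | 72 |

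For onset during infusion the gap is R + 72 − max(R, 72) = min(R, 72). For onset after infusion it is always 72 h, provided the table's trigger covers such onset.

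**When an on-time dose is affected.** Let D be the hours from onset to the next planned dose, with D at least 72. The list allows the dose on time if R ≤ D; the table allows it if R ≤ D − 72. They differ only when D − 72 < R ≤ D. Because R cannot exceed 168, they cannot differ once D reaches 168 + 72 = 240 h.

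- Cycle 1 has tarlatamab in weeks 1, 2 and 3 (Tables 11-5 to 11-7). Assuming 168 h between doses and onset on the dosing day, the rules differ for R above 168 − 72 = 96 h and up to 168 h.
- Using the full 1-day visit window for cycles 1 and 2 (Table 1-2, footnote b), the dose can fall at 168 + 24 = 192 h. The rules then differ for R above 192 − 72 = 120 h and up to 168 h.
- Later cycles show dosing in weeks 1 and 3 (Tables 1-2, 11-8 and 11-9). Assuming 336 h between doses and onset on the dosing day, D = 336, which exceeds 240, so an on-time dose is unaffected.

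**Alternative readings of the table.** The 72 hours may attach to the delay instead of to the time at grade 1 or less, and treatment may mean the infusion only. Counting such a delay from onset:

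| 72 hours attach to | Table's trigger | Gap, onset during infusion | Gap, onset after infusion |
|---|---|---|---|
| time at grade ≤ 1 | any CRS on treatment | min(R, 72) | 72 |
| time at grade ≤ 1 | infusion only | min(R, 72) | table silent |
| delay | any CRS on treatment | 0 | max(0, 72 − R) |
| delay | infusion only | 0 | table silent |

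Only the last combination leaves no difference between the two texts.

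**The case against.** The strongest reply is that the table is ambiguous and, on one reading, agrees with the list. Tables 6-6 and 6-8 count their 72 hours from first observation of the event, which supports attaching the 72 hours to the delay. The grade 2 row tells the site to interrupt the infusion, which hints that treatment may mean infusion. This stands as a possible reading. It removes the conflict for onset during infusion, but not the uncertainty about later onset.

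A second reply is that the medical monitor is consulted in every grade 3 case. Within the dose-limiting toxicity window, grade 3 CRS is not among the listed exceptions (Section 6.2.1.4), so Section 6.2.2.1.3 also calls for withholding and a joint judgement that restart is safe. This limits divergence between sites. It does not tell the monitor which timing applies; the monitor's exception in the grade 3 row concerns dose, not timing.

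A third reply is that present exposure is small. Enrollment ended in January 2023 (Section 4.1), while this protocol is dated June 2024, so cycle 1 dosing should be over. In the first-in-human monotherapy study (Section 2.2.2.3), grade 3 or higher CRS occurred in 1.2% of Part A1 and in none of Part A2, and CRS typically did not recur after cycle 1. This bears on severity, not on whether the texts differ.

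A reader might go further in three ways that the documents do not support:

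- **That grade 3 restarts more easily than grade 2.** The grade 2 default is "delay the next tarlatamab dose until the event resolves to CRS grade ≤ 1 for no less than 72 hours", but that row also lets the next planned dose proceed after discussion with the medical monitor. Grade 3 carries further restrictions of its own, including permanent discontinuation after two separate events.
- **That the instructions are opposite.** The list permits; it does not require an earlier dose. Since R + 72 is at least max(R, 72), a site that follows the table also meets the list's timing.
- **That the rules conflict in 43% of cases.** The ratio (168 − 96)/168 = 43% is a share of clock hours, not a probability. It assumes a redacted interval and ignores the visit window; with the window it is (168 − 120)/168 = 29%.

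**Conclusion.** The inconsistency is real and sits in current protocol text. Two restart rules for the same event differ in the start of the 72 hours and in the trigger, with no stated precedence. On the plain reading the earliest permitted dose can differ by up to 72 hours. An on-time dose is affected only when recovery falls within about 72 hours of that dose, so chiefly in the short cycle 1 intervals. These sizes rest on assumed recovery times and dosing intervals, because the documents give no recovery distribution and the exact dosing days are redacted. How often the difference would have mattered cannot be stated. Given the role of the medical monitor and the end of enrollment, this is a wording reconciliation and not a must-fix defect.

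**What to change.** Reconcile the Table 6-4 grade 3 row with the restart list, so that Section 6.8.1 states one start point for the 72 hours and one scope (onset during infusion only, or any CRS on treatment). State the rule once and have the other place refer to it. Which start point and scope to keep is a clinical decision for the sponsor, on which this review takes no position. The cost is about one line of protocol wording; no analysis, sample size or data collection changes.
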